8.4 Statistical analyses

Effectiveness and safety endpoints are provided in [Sections 2.2.1 to 2.2.4](#).

The sponsor will finalize the SAP prior to database lock. Deviations from the analyses outlined in this protocol will be documented in the SAP within a section discussing changes to the planned analyses.

8.4.1 Effectiveness analyses

8.4.1.1 Primary effectiveness endpoint

The primary effectiveness endpoint is the proportion of responders with \geq 1-grade improvement of both jawlines on the MJAS from baseline to Week 12.

Two hypothesis tests will be performed for the primary endpoint, in a sequential order. The first hypothesis is to demonstrate at least 50% of treated subjects are responders and the second hypothesis is to compare the treatment group with the control group. Each hypothesis test is a one-sided test at a significance level of 0.025.

Hypothesis test 1:

[figure not shown]
$$H_{01}: P_{\text{treatment}} \leq 50\%$$

$$H_{11}: P_{\text{treatment}} > 50\%$$

Hypothesis test 2:

$$H_{02}: P_{\text{treatment}} \leq P_{\text{control}} \quad H_{12}: P_{\text{treatment}} > P_{\text{control}}$$

For hypothesis testing of at least 50% of treated subjects are responders (H_{01} versus H_{11}), the binomial test will be utilized and for testing the statistical superiority of treatment over control (H_{02} versus H_{12}), the Fisher's exact test will be used.

[REDACTED]

[REDACTED]

[REDACTED]

8.4.1.2 *Secondary effectiveness endpoints*

[figure not shown]
- For the FACE-Q satisfaction with the lower face and jawline assessment, among treated subjects, sum scores and the equivalent Rasch-transformed scores will be summarized using descriptive statistics [REDACTED]
- The investigator GAIS for treated subjects will be descriptively summarized at Week 12 using counts (n) and percentages (%) for each GAIS category [REDACTED]

[figure not shown]
[REDACTED] The investigator GAIS will be evaluated relative to baseline.
- The subject-rated GAIS for treated subjects will be summarized at Week 12 using counts (n) and percentages (%) for each GAIS category [REDACTED]

[figure not shown]
[REDACTED]
The subject-rated GAIS will be evaluated relative to baseline.

[figure not shown]
- The proportion of responders in the treatment group and the untreated control group at Week 12, according to the MJAS [REDACTED] will be summarized using counts and percentages. Treatment response is defined as \geq 1-point improvement [REDACTED]

[figure not shown]
8.4.1.3 [REDACTED]

[figure not shown]

8.4.2 Safety analyses and endpoints

Nature, frequency, and severity of AEs and SAEs will be recorded. All AEs and SAEs will be descriptively summarized by treatment and control/delayed-treatment groups according to type, duration, severity, relationship to study device, and the need for touch-up (for those in the treatment and control/delayed-treatment groups), and/or retreatment (for those randomized to the treatment group).

[figure not shown]
The assessment of safety will be based mainly on the frequency of AEs and SAEs. Only treatment-emergent AEs (TEAEs) will be summarized for each treatment group (as applicable) by the incidence of at least one event, the number of events, and the incidence using Medical Dictionary for Regulatory Activities (MedDRA) preferred terms (PTs) within the system organ classes (SOCs). AEs will be coded according to MedDRA.

8.5 Special statistical / analytical issues

8.5.2 *Interim data reporting*

Data listings pertaining to annual reporting updates to the FDA will be produced as necessary. The annual reports will contain enrollment updates (i.e., number of subjects recruited at each site, number screened and enrolled, number randomized, etc.), subject disposition, and safety listings.

9 ETHICS AND ADMINISTRATIVE PROCEDURES

9.1 Ethical considerations

This study will be performed in accordance with the principles outlined in the Declaration of Helsinki and in compliance with the standards for Good Clinical Practice described in ISO 14155, the Code of Federal Regulations, and any applicable regional or national laws and regulations. The study will adhere to all applicable subject privacy requirements.

All required approvals, favorable opinions, or additional requirements of the appropriate IEC, IRB or other regulatory authority will be obtained prior to initiation of the trial.

The investigator and all study personnel will conduct the study in compliance with this protocol. The investigator will ensure that all personnel involved in the conduct of this study are qualified to perform the assigned study responsibilities. Investigators will adhere to all applicable study reporting requirements.

9.2 Informed consent

Written informed consent must be obtained from every subject or his/her legal representative prior to the initiation of any screening or study procedures. The investigator will follow a standard process for obtaining consent that complies with all applicable regulatory requirements. If applicable, a certified translation of the informed consent form into the relevant local language will be provided. The original and any amended signed and dated ICF must be retained at the study site; and a copy must be given to the subject or subject's legally authorized representative(s).

It is not anticipated that members of a vulnerable population will participate in this study.

If the ICF is amended during the study, the investigator must follow all applicable regulatory requirements pertaining to approval of the amended ICF by the IEC/IRB and use of the amended form (including for ongoing subjects).

During the course of the study, the subject will be informed in a timely manner if information becomes available that may be relevant to the subject's willingness to continue participation in the study. In case of AEs, the subject should inform the investigator, who then will make a judgment whether continuing in the study serves the subject's best interests. The subject, however, is free to withdraw consent at any time and for any reason, whether expressed or not.

Each ICF will include contact information (with a phone number) the subject should use to communicate any medical concerns 24 hours a day. Each ICF will also include the contact information for an ophthalmologist and an oral surgeon, who are identified by the Investigator, for instances in which a subject requires evaluation by an ophthalmologist (e.g., subjects experiences sudden visual changes following treatment injections) and/or referral to an oral surgeon.

9.3 Confidentiality of subject information

Subject anonymity is to be maintained during the study. Subjects will be identified by an assigned number on all study documentation. Documents that identify the subject must be maintained in strict confidence by the investigator to the extent permitted by applicable laws and regulations, unless their disclosure is necessary to allow auditing by regulatory authorities, the sponsor, or the sponsor's designee.

Subject medical information obtained during the study is confidential. At a subject's request, the subject's medical information may be provided to the subject's personal physician or other appropriate medical personnel. Disclosure of subject medical information to third parties other than those noted above is not permitted.

9.4 Study monitoring

Study monitoring will conform to all applicable regulatory standards and guidelines. The sponsor or designee will monitor the study through periodic site visits to verify the following:

- Data authenticity, accuracy, and completeness.
- Protection of subject rights and safety.
- Conduct of the study is in accordance with the currently approved protocol and all applicatory regulatory requirements and guidelines.

Investigators agree to grant access to all relevant documents and provide support at all times for study monitoring activities. Study monitoring activities will be performed in a manner that ensures maintenance of subject confidentiality ([Section 9.3](#)).

9.5 Data quality assurance

9.5.1 *Standardization procedures*

Standardization procedures will be implemented to ensure accurate, consistent, complete, and reliable data, including methods to ensure standardization among sites (e.g., training,

newsletters, investigator meetings, monitoring, centralized evaluations, and validation methods).

This study will be monitored regularly by a qualified monitor from the sponsor or its designee according to GCP guidelines and the respective SOPs (see [Section 9.4](#)).

9.5.2 *Data management*

The investigator will prepare and maintain complete and accurate eCRFs recording all observations and data pertinent to the study for each subject. Data reported on eCRFs should be derived from source documents and must be consistent with the sources from which they derive. Investigators will sign and date the eCRFs as appropriate to verify the accuracy of the reported data. It is the responsibility of the Investigator to ensure that all data are submitted to the sponsor in a timely manner.

9.5.3 *Data review and clarification procedures*

All data required by this clinical study protocol are to be entered into a validated database. Individual subject data is to be recorded in eCRFs within 5 days of each study visit.

By signing and dating the eCRFs, the investigator is confirming that all investigations have been completed and conducted in compliance with the clinical study protocol, and that reliable and complete data have been entered into the eCRFs.

If corrections in the questionnaires are necessary, the subject should be instructed to make a correction by drawing only a single line through the error, leaving the incorrect entry legible. The subject should date and initial the correction. The investigator should not make any changes to these documents.

Essential documents should be retained per applicable regulations and as instructed by the study sponsor. Essential documents at the investigational site include but are not limited to:

- Subject files
- Subject identification code list
- A copy of the study protocol and any amendments
- Investigator's copies of the eCRFs and any associated subject-related source data
- Signed ICFs
- Copies of all direct correspondence with the IEC/IRB and with the regulatory authority(ies), and with the sponsor

- Copies of investigational device disposition records

Study documents may not be destroyed by study site personnel prior to the end of the required retention period as specified by local regulations. The PI or the institution must inform the sponsor in due time if the PI leaves the institution during the retention period. This rule also applies when the institution closes within the retention period.

9.5.4 *Study auditing*

To ensure compliance with applicable standards and regulations, the sponsor, IEC/IRB, or regulatory authorities may conduct a quality assurance assessment or audit of site records at any time during or after completion of the study. In the event of an audit, investigators must grant access to all relevant documents (including source documents, electronic records, and other applicable study documentation) and provide support at all times for auditing activities.

9.6 Record retention

Upon closure of the study, the investigator must maintain all study site records in a safe and secure location. The investigator is responsible for the integrity, retention, and security of all study-related records. The investigator must ensure that any reproductions of the original records are legible and provide a true and accurate copy of the original. Accurate, complete, and current records must be stored in such a way as to permit easy and timely retrieval for the sponsor or any applicable regulatory authorities.

The sponsor will inform the investigator of the time period for retaining these records to comply with all applicable regulatory requirements, with the minimum retention time being the longest of those times dictated by institutional requirements, local laws or regulations, or the sponsor's standard procedures. The investigator must notify the sponsor in the event of any changes to archival arrangements due to withdrawal of the investigator's responsibility for keeping study records to ensure that suitable arrangements for the retention of study records are made.

9.7 Publication policy

The study protocol, study data, and information related the study or the sponsor's products or research programs are to be kept confidential and may not be disclosed without the consent of the sponsor. The investigators have the responsibility to provide complete study data, records, and reports for inspection by the appropriate regulatory authorities, the sponsor, or the IEC/IRB, as appropriate.

The investigator agrees that the results of this study may be used for submission to national or international registration and supervising authorities. The sponsor may disclose the information obtained during the study to regulatory authorities or other personnel as required. If necessary, the sponsor may disclose the names, contact information, and qualifications of all investigators as well as their roles in the study. Upon completion of the study, publication or disclosure of the study results is to follow the terms contained in the sponsor's publication policy.

9.8 Financial disclosure

The US FDA Financial Disclosure by Clinical Investigators (21 CFR 54) regulations require sponsors to obtain certain financial information from investigators participating in covered clinical studies. By participating in the study, the investigator agrees to provide the required financial information and to promptly update the sponsor with any relevant changes to this financial information throughout the course of the study and for up to one (1) year after its completion if necessary.

9.9 Investigator compliance

The investigator will conduct the study in compliance with the protocol provided by the sponsor and in accordance with all relevant regulatory guidelines and requirements.

Modifications to the protocol should not be made without the agreement of the investigator and sponsor. The sponsor will submit all protocol modifications to the appropriate regulatory authority in accordance with applicable regulations. All protocol modifications require written IEC/IRB approval/favorable opinion, except in the case of an immediate hazard to subjects.

If an immediate deviation from the protocol is required to eliminate an immediate hazard to subjects, the investigator must contact the sponsor, if possible, to discuss the planned course of action. The investigator must thoroughly document any departure from the protocol and submit appropriate documentation to the sponsor without delay.

11 APPENDICES

1 LIST OF ABBREVIATIONS

AE	Adverse event
ATC	Anatomical Therapeutic Chemical
BMI	Body mass index
CSP	Clinical study protocol
CSR	Clinical study report

DMP	Data management plan
DRM	Data review meeting
eCRF	Electronic case report form
FDA	Food and Drug Administration
GAIS	Global aesthetic improvement scale

ITT	Intent-to-treat
MAR	Missing at random
MedDRA	Medical Dictionary for Regulatory Activities
MI	Multiple imputation
MJAS	Merz jawline assessment scale
MNAR	Missing not at random
MVT	Missing value treated as failure
n	Number of non-missing observations
OC	Observed cases
PDF	Portable document format
PP	Per protocol population
PT	Preferred term
SAE	Serious adverse event
SAP	Statistical analysis plan
SAS®	Statistical Analysis System
SD	Standard deviation
SOC	System organ class
TFLs	Tables, figures, and listings
TEAE	Treatment emergent adverse event
TOC	Table of content

2 GENERAL AND TECHNICAL ASPECTS

The objective of this statistical analysis plan (SAP) is to specify the statistical analyses in greater detail than stated in the clinical study protocol so as to be precise enough to serve as a guideline for statistical programming and creation of tables, figures, and listings (TFLs).

This statistical analysis plan is based on the clinical study protocol (version 4.0), dated 20-July-2018.

All programs will be written using SAS version 9.4 or higher. Individual SAS programs will be written for all tables, figures, and listings. All outputs will be transferred into PDF files. The PDF files will be generated separately for the tables and figures of section 14 and the listings of section 16 of the appendix of the clinical study report (CSR). Each PDF file will include the corresponding table of contents, preceding the content of the file.

[REDACTED] TFLs will be applied and adapted to study specific requirements as specified in the clinical study protocol (CSP) and any amendments, if applicable.

3 CLINICAL STUDY DESIGN AND OBJECTIVES

3.1 Clinical Study Design

This is a 60-week, prospective, multicenter, randomized, controlled, [REDACTED] pivotal clinical study to investigate the effectiveness and safety of Radiesse (+) to improve the contour of jawline by adding to the jawline. Approximately 180 subjects with a grade of 2 or 3 on the MJAS will be enrolled into the study. [REDACTED]

[REDACTED] Subjects will be enrolled at up to 15 sites in the United States. [REDACTED]

At the baseline visit, enrolled subjects will be randomized (2:1 allocation ratio) to either treatment with Radiesse (+) or to untreated control. Those allocated to the control group at baseline will remain untreated until assessment of the primary effectiveness endpoint at Week 12; these subjects will then be eligible for delayed treatment with Radiesse (+) in the jawline at Week 12 and will be followed for 48 weeks post-treatment. [REDACTED]

[figure not shown]
[REDACTED] Subjects who achieve a ≥ 1 -point improvement on the MJAS [REDACTED] may have a touch-up [REDACTED]

[REDACTED]. The primary effectiveness endpoint will be assessed 12 weeks post-treatment. Subjects randomized to the treatment group at baseline will have the option for re-treatment with Radiesse (+), upon agreement between the subject and the investigator, at Week 48 and will then be followed for an additional 12 weeks, for a total study duration of 60 weeks. Subjects who do not receive a re-treatment at Week 48 will also be followed until Week 60.

Subjects randomized to the control group at baseline will remain untreated until completion of the primary endpoint assessment at Week 12. After all primary endpoint assessments have been completed these control subjects will be treated with Radiesse (+) (i.e., delayed treatment) and will then be followed 48 weeks post-treatment. These delayed-treatment subjects will be required to have a touch-up in [REDACTED] if a subject does not achieve a ≥ 1 -point improvement on the MJAS [REDACTED]

[REDACTED]. Subjects who achieve a ≥ 1 -point improvement on the MJAS [REDACTED]

may have a touch-up [REDACTED] for further optimal correction at the discretion of the treating investigator. Control subjects will not be offered re-treatment.

3.2 Clinical Study Objectives

[figure not shown]
Effectiveness Objective:

The primary objective of the study is to demonstrate the effectiveness of Radiesse (+) following deep (subdermal and/or supraperiosteal) injection to improve the contour of jawline by adding volume to the jawline.

Safety Objective:

The safety objectives include the identification and description of adverse events (AEs), and serious adverse events (SAEs) during the course of the study. [REDACTED]

4 DETERMINATION OF SAMPLE SIZE

The statistical power calculation software, nQuery Advisor Version 7.0, was used for sample size calculations.

5 ANALYSIS SETS

The following analysis sets will be defined for all statistical analyses of this clinical study:

Intent-to-Treat (ITT)

The Intent-to-Treat (ITT) population will consist of all randomized subjects. This will be the primary population used for the effectiveness analyses. All effectiveness endpoints will be analyzed as randomized

Safety Evaluation Set (SES)

The SES is the subset of all subjects who were exposed to study medication at least once. All safety endpoints and exposure data will be analyzed as per actual treatment received.

Per Protocol Population (PP)

The Per Protocol (PP) population is a subset of subjects in the ITT population without major protocol deviations. Final determination of what constitutes major or minor protocol deviations will be made prior to database lock.

[REDACTED]

Major protocol deviations will be finalized during the Data Review Meeting that will be carried out prior to database lock.

Populations for Primary and Secondary Effectiveness Endpoint Analyses

The primary and secondary effectiveness endpoints will be summarized using the ITT population, and additionally, for sensitivity purposes, on the PP.

[REDACTED] Additional details of the use of analysis populations are provided below in the Statistical Analysis Methods section. All safety endpoints will be summarized using the SES.

6 ENDPOINTS FOR ANALYSIS

6.1 Effectiveness Endpoints

6.1.1 *Primary effectiveness endpoint*

[figure not shown]
Comparison of the responder rate between the treatment group and the untreated control group at Week 12, according to the Merz Jawline Assessment Scale (MJAS) [REDACTED]. Treatment response is defined as ≥ 1 -point improvement [REDACTED]. The study device will be clinically effective if at least 50% of treated subjects are responders.

[figure not shown]
6.1.2 *Secondary effectiveness endpoints*

[figure not shown]
- [REDACTED] FACE-Q satisfaction of the lower face and jawline for treated subjects [REDACTED] as average percent change from baseline to Week 12. [REDACTED]
- [REDACTED] Global Aesthetic Improvement Scale (GAIS) scores for treated subjects at Week 12, as completed by the treating investigator. [REDACTED]
[REDACTED]
- [REDACTED] GAIS scores for treated subjects at Week 12, as completed by the subject. [REDACTED]
- [REDACTED] responder rates in the treatment group and the untreated control group at Week 12, according to the MJAS [REDACTED]
[REDACTED]
[REDACTED]
Treatment response is defined as ≥ 1 -point improvement [REDACTED]
[REDACTED]
[REDACTED].

6.1.3 [REDACTED]

[REDACTED]

6.2 Safety Endpoints

6.2.1 *Primary safety endpoints*

- Incidence and nature of device- and/or injection-related AEs and SAEs observed during the study.

6.2.2 [REDACTED]

7 STATISTICAL ANALYSIS METHODS

7.1 Effectiveness Endpoints

The primary effectiveness analysis and the analysis of the secondary effectiveness endpoints will be based primarily on the ITT and additionally, for sensitivity purposes, on the PP. [REDACTED]

[REDACTED] Statistical tests on the primary effectiveness endpoint will be conducted as a one-sided hypothesis to determine evidence of between-treatment differences.

For summary purposes, continuous variables (values and changes from baseline) will be summarized by n, mean, standard deviation (SD), median, minimum, and maximum. For qualitative variables, absolute and percent frequencies (n, %) and, if applicable, shift tables will be displayed. For all test statistics used for analyzing the effectiveness endpoints, p-values will be used either for inferential or for descriptive purposes, as appropriate.

Change from baseline is defined as post-baseline value minus the corresponding baseline value; percent change from baseline is defined as change from baseline divided by the corresponding baseline value, expressed in percentage.

P-values will be reported to four decimal places (e.g. p=0.0375). P-values below 0.0001 will be presented as '<0.0001'.

7.1.1 Primary Effectiveness Endpoint

The primary effectiveness endpoint, the proportion of responders, subjects with \geq 1-grade improvement [REDACTED] on the MJAS from baseline to Week 12 will be summarized as counts and percentages for the treatment and control groups.

Two hypothesis tests will be performed for the primary endpoint, in a sequential order. The first hypothesis is to demonstrate at least 50% of treated subjects are responders and the second hypothesis is to compare the treatment group with the control group. Each hypothesis test is a one-sided test at a significance level of 0.025.

[figure not shown]
Hypothesis test 1:

[figure not shown]
$$H_{01}: P_{\text{treatment}} \leq 50\% \quad H_{11}: P_{\text{treatment}} > 50\%$$

Hypothesis test 2:

$$H_{02}: P_{\text{treatment}} \leq P_{\text{control}} \quad H_{12}: P_{\text{treatment}} > P_{\text{control}}$$

For primary hypothesis testing of at least 50% of treated subjects are responders (H_{01} versus H_{11}), the binomial test will be utilized. For primary testing of statistical superiority of treatment over control (H_{02} versus H_{12}), the Fisher's exact test will be used.

[figure not shown]

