4.1 Number of subjects and sites

Approximately 180 subjects will be enrolled, with approximately 120 subjects in the treatment group and 60 subjects in the control/delayed-treatment group. Subjects will be enrolled from up to 15 sites in the United States.

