8 STATISTICAL METHODS

This section describes the statistical analyses foreseen at the time of study planning. Further details on the statistical and analytical aspects will be presented in the statistical analysis plan (SAP) that will be prepared and completed prior to database lock.

Any deviations from planned analyses, the reasons for such deviation, and all alternative or additional statistical analyses that may be performed before database close will be described in amendments to the clinical study protocol and/or the SAP. All deviations and/or alterations will also be summarized in the clinical study report.

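### Does the primary decision rule need rewriting because the 50% criterion, the form of the binomial test and the reading of test 2 after a failed test 1 are not spelled out?

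*SAP*

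**What the plan says.** SAP 6.1.1 defines the primary endpoint as the treatment-versus-control comparison of Week 12 responder rates on the MJAS, and adds: "The study device will be clinically effective if at least 50% of treated subjects are responders".

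SAP 7.1.1 then gives the tests: "Two hypothesis tests will be performed for the primary endpoint, in a sequential order". The first has null hypothesis H01, treated response of 50% or less. The second has H02, treated response no higher than control. Each is one-sided at 0.025. On the choice of test for H01 and then H02 it reads "the binomial test will be utilized. For primary testing of statistical superiority of treatment over control", and the test it goes on to name for H02 is Fisher's exact test. Protocol 8.4.1.1 matches this: "the binomial test will be utilized and for testing the statistical superiority of treatment over control" is by Fisher's exact test.

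The general text of SAP 7.1 says the primary tests are "conducted as a one-sided hypothesis to determine evidence of between-treatment differences", and that for the effectiveness endpoints as a whole "p-values will be used either for inferential or for descriptive purposes, as appropriate".

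Protocol 4.1 plans "approximately 120 subjects in the treatment group" and 60 in the control group.

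**The concern.** Four features of the text look loose for the primary decision rule of a pivotal trial.

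- **The 50% criterion.** SAP 6.1.1 names no test. Read literally, 60 responders out of 120 would meet it, and a device with a true rate of exactly 50%, which lies inside H01, would pass more than half the time.
- **The form of test 1.** Fisher's test is called exact and the binomial test is not. A programmer could use a normal approximation, which at some sample sizes needs one responder fewer and exceeds the stated 0.025.
- **A failed test 1.** No visible sentence says what the Fisher p-value then means, or whether success needs both tests. The general remark that p-values are inferential or descriptive as appropriate does not settle it. A sponsor who missed the 50% bar but clearly beat an untreated control might be tempted to claim success on the second test.
- **The description of the tests.** A one-sample test against 50% is not a comparison between treatments, as SAP 7.1 puts it.

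At stake would be the type I error of the primary claim and the reading of a split result.

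**Working it through.** **Inputs.** One-sided level 0.025 per test and p0 = 0.50 (SAP 7.1.1); 120 treated and 60 control, both approximate (Protocol 4.1). The power, the assumed responder rates and the dropout allowance are not visible, so the sample size cannot be reproduced. All 120 treated subjects are assumed evaluable. Control rates and true response rates below are assumptions, shown as ranges.

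**Step 1: cut-off for test 1 at n = 120.**

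- Exact form: the smallest r with P(X ≥ r) ≤ 0.025, X ~ Binomial(120, 0.5). P(X ≥ 71) = 0.0274 and P(X ≥ 72) = 0.0177, so 72 responders (60.0%) are needed.
- Normal approximation, uncorrected: z = (r − 60)/√(120 × 0.25) = (r − 60)/5.477. At r = 71, z = 2.008 and the nominal p is 0.0223. It therefore rejects at 71 (59.2%), with a true size of 0.0274.
- Normal approximation, continuity-corrected: z = (r − 0.5 − 60)/5.477. At r = 71, z = 1.917 (p = 0.0276, no rejection); at r = 72, z = 2.100 (p = 0.0179). The cut-off is 72, as for the exact form.

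**Step 2: other arm sizes.** From 108 to 126 treated (19 sizes), the exact and uncorrected forms differ at 8: 109, 111, 113, 116, 118, 120, 122 and 124. At those the uncorrected form's true size is 0.0254 to 0.0297. The corrected form agrees with the exact form at all 19.

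**Step 3: how often the choice would matter.** At n = 120 the forms disagree only if exactly 71 subjects respond.

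| True response | P(exactly 71) | Power, exact | Power, uncorrected z |
|---|---|---|---|
| 50% | 1.0% | – | – |
| 55% | 4.8% | – | – |
| 60% | 7.3% | 0.540 | 0.612 |
| 65% | 3.1% | 0.892 | 0.923 |
| 70% | 0.3% | 0.993 | 0.996 |

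**Step 4: the 50% sentence.** The literal reading passes at 60 of 120, and P(X ≥ 60) at a true rate of 50% is 0.536. Against the exact test the gap is 72 − 60 = 12 responders. But SAP 7.1.1 repeats the same 50% statement, labels it H01 versus H11, and assigns it a test and a level. Section 6 of the SAP lists endpoints and section 7 gives the methods, so the operative rule is the one in 7.1.1.

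**Step 5: reading test 2.** If H02 is tested only after H01 is rejected, or if success needs both, the chance of a false claim stays within 0.025. Only if either test alone could count as success does the bound rise to 0.025 + 0.025 = 0.05. Running the tests in sequence, each at the full 0.025, fits the gated reading and not the either-or reading.

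**Step 6: split results.** With 18 of 60 control responders Fisher's test rejects from 56 of 120 treated; with 24 of 60, from 69. Both are below 72, so test 1 can fail while test 2 is significant. The probability of that, with an assumed control rate of 10% to 30%, is 0.71–0.84 at 55% true response, 0.42–0.46 at 60%, 0.10–0.11 at 65%, 0.007–0.008 at 70% and 0.0001 at 75%. With a control rate of 40% it is 0.29, 0.21, 0.06, 0.004 and 0.0001. These figures describe how often a weaker device misses the 50% bar. They would be the same if the gate were written out in full.

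**The case for a change.** The strongest case for a change is that the SAP is meant to be precise enough to guide programming, and that this is the primary decision rule. A few sentences before database lock would name the exact test, link 6.1.1 to H01 and state the gate. They would cost no patients and, since Protocol section 8 leaves further statistical detail to the SAP, no protocol amendment. The uncorrected approximation would breach the stated level at 120, and because 120 is approximate, nobody can count on a final size at which the forms agree. The split result is plausible if true response is below about 70%, and its reading is best fixed before the data are seen.

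The arithmetic stands, and so does the fact that these sentences are not visible. The inference that the plan is therefore deficient does not. The harm from the form of test 1 needs an analyst to choose the one version that is neither exact nor corrected. The harm from test 2 needs a sponsor to read a declared sequence as two separate chances at success. The general remark on p-values covers every effectiveness endpoint, many of them descriptive, and is not a rule for the second primary test. The mention of between-treatment differences is a loose introductory phrase that the formal hypotheses override.

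Absence also cannot be shown here. Blacked-out blocks follow the test sentence in Protocol 8.4.1.1, a figure is missing after the same sentence in SAP 7.1.1, and parts of SAP 6.1.1 and 7.4 are blacked out.

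One point keeps some force: a sentence saying whether success needs both tests would help a reader of the public text. That is editorial.

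**Conclusion.** No change follows. This is a gap in wording that a competent analyst fills correctly: the 50% criterion is H01, the binomial test is exact, and H02 is read inferentially only after H01 is rejected. On that reading type I error is held at one-sided 0.025, no stated figure is wrong, and the planned order is valid.

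The largest numerical effect is one responder (71 against 72 of 120) at 8 of 19 plausible arm sizes, and only under an uncorrected approximation that the plan does not mention. Its chance of changing the decision at n = 120 is at most 7.3% over the true rates tabulated, and 0.3% at 70%. The large split-result probabilities do not measure a defect, because writing the gate out would not alter them.

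This rests on all 120 treated subjects being evaluable, on assumed control and response rates, and on the ordinary meaning of a sequential pair of tests. If the unpublished text adopted an uncorrected approximation, or let either test alone count as success, the conclusion would need another look.
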